#### 12. Risks and Benefits:

General: While subjects are participating in this study, they will temporarily forgo the opportunity to receive routine clinical psychiatric care in the community (i.e. patients are asked to maintain their treatment regimen throughout the study). This will be clearly explained to all patients, along with the treatment strategies that are generally used in patients with PTSD. Patients will also be told that riluzole is available for prescription by clinicians in the community; however, it has not received FDA approval for the indication of PTSD.

Screening and evaluation: The risks and discomforts of the screening and evaluations are minimal. No discomfort is expected to be associated with the physical examination or intake interview with the study staff other than the possible stress of answering personal questions. Subjects will be answering questions about their symptoms of PTSD and filling out questionnaires. They may find this process to be inconvenient, uncomfortable or upsetting. The psychological testing may include personal questions about previous experiences. The questions will be asked in a private room. Subjects will be informed that they do not have to answer any question that they do not want to answer. Subjects will also have the option to discuss their concerns with someone on the research staff. One or more individuals will be available to talk to the subjects should they become distressed during an interview or while filling out questionnaires.

Risks of ECG test: Sometimes the adhesive pads used to attach the leads for recording the electrical activity of the heart (ECG) can cause skin irritation. Such irritation usually clears without treatment.

Blood drawing: Blood samples are taken from a vein in the inside of the elbow or lower arm. Blood collection is done using a disposable needle or syringe. The risks or side

effects associated with taking blood from a vein are bruises, local irritation (swelling) with itching, slight bleeding and inflammation. In rare cases, it may result in thrombosis (blood clots) or an infection. Insertion of the needle can cause localized pain or pain at the needle puncture site. Subjects may feel slightly weak or lightheaded, or faint. Occasionally, in rare cases, inserting the needle can result in injury to a nerve. Subjects are closely monitored and checked for these or other symptoms and we will take appropriate measures if they occur. Normally these problems improve with time and no additional medical treatment is needed. Using trained personnel, as well as using sterile conditions minimizes these risks.

The total maximum quantity of blood that may be taken over the entire course of this study is less than 300 ml. This is 1.27 cups of blood. The blood is taken slowly over the course of the study. As a comparison, during a blood donor session, 450 mL (or less than 2 cups) of blood is taken in one visit.

Delay in treatment: By participating in this study, subjects are likely to experience a delay in starting other treatment due to the thorough diagnostic evaluation. Furthermore, since it is unknown whether riluzole is effective in the treatment of PTSD, participation in this trial could delay potentially effective therapy. During this period, it is possible that subjects' conditions could worsen and lead to increased disturbances in mood, sleep, appetite, and cognition. This could result in work loss, loss of social function, and possibly increased risk of suicide. However, the risk should be minimized as there are several safety precautions in place and subjects will remain in close contact with study clinicians.

Riluzole: Most side effects are usually mild and resolve after stopping the drug. The most commonly observed adverse reactions of riluzole, dosed at 100mg/day, in placebocontrolled trials were asthenia (19.2%), nausea (16.3%), decreased lung functioning (10.2%), headache (7.3%), rhinitis (6.4%), hypertonia (6.1%), hypertension (5.1%), abdominal pain (5.1%), weight loss (4.8%), vomiting (4.2%), dizziness (3.9%), dyspnea (3.8%), pruritus (3.8%), insomnia (3.5%), dry mouth (3.5%), arthralgia (3.5%), back pain (3.2%), anorexia (3.2%), peripheral edema (2.9%), diarrhea (2.9%), increased cough (2.6%), tachycardia (2.6%), flatulence (2.6%), urinary tract infection (2.6%), somnolence (1.9%), vertigo (1.9%), oral paresthesia, and, pneumonia. Cases of interstitial lung disease have been reported in patients treated with riluzole, some of them severe; upon further investigation, many of these cases were hypersensitivity pneumonitis. If respiratory symptoms develop such as dry cough and/or dyspnea, chest radiography should be performed, and in case of findings suggestive of interstitial lung disease or hypersensitivity pneumonitis (e.g., bilateral diffuse lung opacities), riluzole should be discontinued immediately. In the majority of the reported cases, symptoms resolved after drug discontinuation and symptomatic treatment.

Dizziness, diarrhea, anorexia, and circumoral paresthesia occurred more frequently with 200 mg/day riluzole. In a study with approximately 4,000 patients given riluzole for ALS, three cases of neutropenia were reported within the first two months of treatment. Any

new medication has the potential for a rare, infrequent reaction of hypersensitivity, including anaphylaxis.

Uncommon side-effects: neutropenia – very rarely there is an abnormal drop in the number of white blood cells within the first two months of treatment. Rarely, jaundice is a side effect as well. Riluzole has also been found to cause elevations in serum aminotransferase even in patients without a history of liver disease. Experience with riluzole in 800 patients with ALS demonstrated that approximately 50% of riluzole treated patients experienced at least one ALT/SGPT level above the ULN, 8% had elevations > 3 x ULN, and 2% > 5 x ULN. A single non-ALS patient with epilepsy treated with concomitant carbamazepine and phenobarbital experienced marked, rapid elevations of liver enzyme with jaundice four months after starting riluzole that returned to normal seven weeks after treatment discontinuation. Another rare side effect is pancreatitis. It is estimated that pancreatitis can occur in 4.5/10000 treated patients. A recently published Cochrane Database Systems Review  states "Adverse effects from riluzole are relatively minor and for the most part reversible after stopping the drug" in the plain language summary.

Riluzole is Pregnancy Category C: Riluzole is detected in breast milk of rodents, and the recommendation from the PDR is for riluzole not to be used. Women who are breastfeeding will be excluded from enrollment. If a woman becomes pregnant during the study, the study medication will be discontinued.

Worsening of symptoms and suicide risk: At any time during the study, subjects may experience a worsening of symptoms and possibly have serious thoughts of suicide or of harming themselves.

Unidentified or unforeseen risks: Participation in this study may involve risks that are not known at this time.

**Minimizing Risks:** We describe below the manner in which the above-mentioned risks will be minimized.

Subject Recruitment and Consent: Subjects will be recruited through flyers, public advertisement (newspaper, radio, internet posting), by word of mouth, contact with community service groups, the NCPTSD's approved screening protocol (KW0003), and clinics and local treatment facilities (e.g., VA Hospital, Community-Based Outpatient Clinics, local private practices). Subjects will be identified via their response to advertisementsand/or internal recruiting through the research clinics. Subjects will be asked to call us at the number provided on the flyers if they are interested in participating in the research study. Subjects will be contacted for follow-up appointments via the most convenient means and personal preference, e.g. telephone. All available research staff is responsible for recruiting potential subjects.

After an initial phone screening, consent forms will be given to all prospective subjects, which detail all aspects of the project. The consent form will include the risks of

participation, assurance of efforts to maintain confidentiality, and will state that patients are free to refuse participation or to withdraw from the project and receive open uncontrolled treatment according to clinical indication, without loss of benefits to which they are otherwise entitled. The informed consent procedures will comply with the standards of the Institutional Review Boards at the VA.

A member of the research team will obtain written consent from the participants after explaining the procedures and risks involved. The original signed consent form is kept in a separate file from the subjects' research chart. The consent makes it explicit that the protocol involves return visits at specified times. Participants are informed of the amount of blood (less than 300mL or 1.27 cups) that will be drawn in the various procedures and the nature of the assays that will be performed. In particular, the consent form indicates that the nature of treatment is determined by the protocol, and that the study is a trial to evaluate efficacy of riluzole. Subjects will be informed that if their clinical condition deteriorates during the study, they may be hospitalized. The consent procedure is viewed as a process rather than a single event, and patients will be encouraged to discuss the study with the research team.

Protection Against Risks: All clinical raters have experience in clinical psychiatric assessment and will make every effort to implement protocol procedures in a sensitive and supportive manner. Research interviews will be interrupted if subjects become distressed or object to answering questions. Other measures to minimize risks include the careful assessment of each subject before the study, and close clinical scrutiny during all aspects of the study. Screening for suicide risk factors and suicidality is described in the research design.

Weekly contact is maintained throughout the clinical trial. A study staff member will call participants, during any week in which there is no clinic visits, to help ensure subject safety and protocol adherence.

We have included safety measures such as discontinuation of the study drug and transition to standard clinical treatment should subjects worsen to a sufficient degree. These precautions are likely to be highly effective in minimizing risks. Subjects may be hospitalized if they have a worsening of their symptoms, including becoming suicidal. In this case or if subjects discontinue study medication they will receive standard short-term clinical treatment as indicated.

Due to the potential of riluzole to cause elevations in serum aminotransferase levels, subjects will have liver function tests performed prior to initiating the trial and monthly for the duration of the study, or more frequently if clinically indicated. Patients with any evidence of clinically significant liver abnormalities or any liver transaminase level > 1.5 x ULN at baseline will be excluded from the study. Subjects will be discontinued from the study if any LFT measure rises above 5 x the ULN once treatment has been initiated. This is the recommendation in the PDR and is what has been used in previous studies. If treatment is terminated due to physical risks, subjects will be followed carefully until resolution of symptoms and treated with the follow up care described in the protocol.

Subjects will also be asked to report any cough, difficulty breathing or chills to the study staff in order to monitor for the possible emergence of interstitial lung disease or hypersensitivity pneumonitis. The study investigator, physician/APRN, and rater ask patients about any new symptoms at every visit.

Suicidal Ideation and Imminent Harm: Despite treatment, people with PTSD may get worse. All communications about suicide and threats are taken seriously. It is important to assess the risk of suicide carefully when working with these individuals. Many subjects may admit to fleeting thoughts of death or briefly wishing for death; these thoughts need to be considered in context of the subject's overall history, along with a consideration of other risk factors for suicide. Study clinicians will assess patients at each visit for suicide risk and potential. Individuals at such risk will be treated appropriately, including options such as increased contact, more frequent clinical visits, or emergent psychiatric hospitalization. Subjects who score > 5 on the MADRS item 10 (suicide) at screening will be excluded from the study. In addition, a serious suicide or homicide risk, as assessed by evaluating clinician will be considered an exclusion criterion.

Throughout the study, any subject who scores  $\geq 5$  on the MADRS item number 10 will be discontinued from the study. Any subject with scores of  $\geq 6$  on the CGI-I will be discontinued from the study.

Subjects will be informed of any important discoveries made during this study, which may affect their condition or willingness to participate in this study by leaving a message (with subject permission) to contact the study team or by letter, if the subject cannot be reached by phone.

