SPECIFIC AIM 1: To provide preliminary data about the efficacy of riluzole treatment in improving PTSD symptoms. *Hypothesis*: PTSD subjects treated with

riluzole (50 mg twice per day for 12 weeks) will have reduction in PTSD symptoms. To examine the efficacy of riluzole we will compare the mean change in the CAPS total score over the course of 12 weeks of riluzole treatment.

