**6. Significance of proposed research:** Our proposed study is the first to examine the effect and feasibility of riluzole treatment for PTSD. Data from this pilot study will inform the design of future larger double-blind controlled studies. For e.g., if PTSD veterans showed full early response to riluzole following 1-4 weeks, this will affect the design of future definitive (likely multisite) studies. While placebo-controlled studies are standard for FDA approval and definitive clinical trials confirming efficacy, an open label approach is appropriate for pilot studies seeking early signals of efficacy and optimal treatment regimen. Pilot open label studies are essential for early phase of drug development.

**7. Experimental subjects**: We anticipate approximately 20 male and female subjects with PTSD, between the ages of 18-75 years, to complete all study procedures. In order to account for screenings failure and subject drop outs, and retain a sample of 20 subjects completing the treatment phase, approximately 50 eligible subjects will be enrolled.

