- 19. Systematic Assessment for Treatment Emergent Events (SAFTEE): The SAFTEE is a commonly used instrument originally developed by NIMH and adapted into a self-report instrument. It examines, in systematic fashion, possible treatment-emergent side effects and probes for specific adverse symptoms, including suicidal thoughts and behaviors, and self-injurious behavior.
- 20. Drug Attitude Inventory- (DAI): The DAI evaluates how attitudes about medications may affect treatment adherence. The items with the most potential for discrimination between dosing compliance and noncompliance are related to subjective 'feeling' factors.
- 21. Perceived Stress Scale (PSS): This is a 10-item self-report questionnaire to assess the severity of perceived stress over the past month.
- 22. Cumulative Adversity Interview (CAI): A multifaceted semi-structured assessment of stressful life events and chronic subjective stress used in research on stress and psychopathology.

Due to the potential of Riluzole to cause elevations in serum aminotransferase levels, liver function tests will be reviewed and monitored for medical significance (marking NCS for results not clinically significant) by the PI, a co-investigator or other medical research personnel (A.P.R.N., R.N. etc.). If any liver transaminase level is > 5X the UNL, the study investigator will be informed and the patient will be discontinued from the study, with appropriate medical follow-up.

PTSD subjects receiving the study medication will be seen weekly. Compliance with study medication will also be assessed weekly and at each visit. Subjects will be given medication diary cards to record the medication that they have taken at each daily dosing interval and the medication that was missed at each dosing interval. Drug accountability will then be done between the medication that was returned and the medication recorded as being taken on the diary cards. A subset of the interviews and measures obtained throughout the study will be repeated at a one-month, in person follow-up. This follow-up will be used to evaluate any lasting effects of the treatment, if any.

The presence of any spontaneously reported side effect or adverse event is carefully documented. Reasons for premature discontinuation of study medication, including intolerable side effects, are recorded; however, all willing subjects continue to return for weekly evaluations as if they remain on study medication.

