#### **Data Analysis**

Descriptive statistics will be calculated prior to statistical analysis. Distributions of quantitative variables will be assessed for normality using normal probability plots and Kolmogorov-Smirnov statistics and transformations or non-parametric methods will be used as necessary. All statistical tests will be two-sided. Uncorrected alpha level of 0.05 will be used for testing the primary hypothesis. Pairwise post-hoc comparisons and tests of secondary outcome measures will be adjusted using Holm-Bonferroni procedure. All analyses will be intent-to-treat. We will using mixed effects regression models, with time effects for the primary outcome variable (CAPS). We do not expect significant moderating effects of alcohol use comorbidity but will assess the interaction between treatment and alcohol use comorbidity and perform follow-up tests as necessary. This approach will be applied to most secondary outcome measures as well. Mixed effects regression models use all available data on each subject, are flexible in modeling the correlation structure of the data and give unbiased results under missing at random

assumptions. In addition to testing the potential moderating effect of comorbid alcohol use described above, we will also perform exploratory analyses to the assess moderating effects of depression, medication status, substance abuse, age, and gender by adding these factors one at a time to the models above and testing interactions between each potential moderator and treatment group. Effects of intermittent missing data due to noncompliance with treatment schedule can also be assessed.

Table 1. Schedule of Study Events\*\*

	1 doie 1. Senedule of Study Events											
Visit	Screeni ng a	Baselin e	1	2&3	4	5,6,&7	8	9,10,11	12	month follow- up		
Day	0	0	7	14&21	28	35,42, & 49	56	63, 70, &77	84	114		
Informed Consent b	X											
Demographics	X											
SCID / MINI	X											
C-SSRS baseline	X											
MGH ATRQ	X											
ETI-SR, KLS, GPELS, CES	X											
M-MACE	X											
Psychiatric Evaluation	X											
BP, Pulse, Resp., Wt., Temp.	X	X	X	X	X	X	X	X	X			
ECG	X											
Physical Exam	X											
СВС	X				X		X		X			
СМР	X				LFTs		LF Ts		LFTs			
Serum Pregnancy (1)/ Urine Pregnancy (2)	X(1)	X (2)			X(2)		X( 2)		X(2)			
Urinalysis	X											
Inclusion/Exclusion	X											
CAPS	X	X °				X (visit 6 only)			X	X		
MADRS	X	X	X	X	X	X	X	X	X	X		
PCL, QIDS-SR, PSWQ, PSQI, SDS, SAFTEE		X	X	X	X	X	X	X	X	X		

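### CAPS scores taken off riluzole and on other treatment can enter the single-arm 12-week change that Aim 1 attributes to riluzole, and no planned analysis sets them apart

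*Combined protocol and SAP*

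**What the plan says.** - **Treatment after stopping.** Section 12, Protection Against Risks, states that "if subjects discontinue study medication they will receive standard short-term clinical treatment as indicated". The same paragraph describes moving subjects who worsen enough to usual clinical care.
- **Follow-up after stopping.** Section 11, C.3, in the text after the list of instruments, says that after early discontinuation "all willing subjects continue to return for weekly evaluations as if they remain on study medication". It then repeats the point, gives safety monitoring as the reason, and adds that non-adherent subjects count as dropouts in the analysis. It does not say what that does to their scores.
- **Analysis.** The Data Analysis section makes every analysis intent-to-treat and models CAPS with time effects, noting that "Mixed effects regression models use all available data on each subject". On testing: "All statistical tests will be two-sided" and "Uncorrected alpha level of 0.05 will be used for testing the primary hypothesis".
- **Interpretation.** Under Specific Aim 1, "we will compare the mean change in the CAPS total score over the course of 12 weeks of riluzole treatment". There is one arm; section 6 argues that "an open label approach is appropriate for pilot studies seeking early signals of efficacy and optimal treatment regimen".
- **Timing.** Table 1 schedules CAPS at screening, at baseline (repeated under a footnoted condition), visit 6 (day 42), visit 12 (day 84) and the one-month follow-up (day 114).

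No section says that CAPS scores taken after the last dose, or after other treatment begins, are excluded, flagged or analysed separately.

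**The concern.** Intent-to-treat protects a randomised comparison because both arms carry their later treatment with them. Here nothing is compared: the time effect is the whole result. While subjects take riluzole, the protocol limits co-treatment. Antidepressants must have been stable for at least 4 weeks, PTSD-focused psychotherapy must have run for at least 8 weeks, and section 12 asks subjects to keep their regimen unchanged. That control lapses once riluzole stops, and the analysis does not respond to the lapse.

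A subject who stops, receives other treatment and improves by day 84 adds to the riluzole change. One who stops and then relapses subtracts from it. Section 6 says the pilot will inform larger trials, and their designers would need to know how much of the change arose on the drug.

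**Working it through.** **1. The plan's own figures.** Section 7 gives about 50 enrolled to retain 20 completers, a combined loss of 1 − 20/50 = 60%. Screening failures and dropouts are not separated, so this is not a stopping rate. No power, SD or effect size is stated, so there is no calculation to reproduce.

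**2. Following one subject.** Take a willing subject who stops at week 4 because of a side effect. Other treatment may begin (section 12). Visits continue (section 11, C.3), so CAPS is due on days 42 and 84. Both scores enter the model (Data Analysis), and the estimate is named as riluzole change (Aim 1). No rule breaks this chain.

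**3. Where the chain is uncertain.** The general C.3 text would keep all willing stoppers in evaluation. Other text may end it:

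| Reason for stopping | Text that may end CAPS or remove it |
|---|---|
| Any | Section 11.B lets assessments stop as well as treatment; early stoppers are seen if possible |
| Cannot tolerate the once-daily dose | Section 11, Dosing: leaves the study; but C.3: withdrawn from medication only |
| Transaminases > 5 × ULN | C.3 and Protection Against Risks: leaves the study |
| MADRS item 10 ≥ 5, or CGI-I ≥ 6 | Section 12, Suicidal Ideation and Imminent Harm: leaves the study |
| 35% rise in CAPS | Section 11.B: listed reason for discontinuing |
| Non-adherence | C.3: a dropout in the analysis, undefined |

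**4. Size of the shift.** Let s be the share of week-12 CAPS scores taken after other treatment began. Let d be how much better those subjects' change is than it would have been on riluzole alone. The shift in the mean is s × d. Neither input is in the documents. Assuming s = 10–20% and |d| = 5–10 points:

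- smallest: 0.10 × 5 = 0.5 points
- largest: 0.20 × 10 = 2 points

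Positive d overstates the change; negative d understates it by the same amount. With no SD of CAPS change given, these points cannot be converted to SD units.

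**5. Effect on the test (upward case only).** A one-sample t-test on change stands in for the model's time effect: two-sided 0.05, 40,000 simulations, true riluzole change of zero. Assumed: 20% or 40% of analysed subjects switch, and the other treatment improves CAPS by 0.5 or 1.0 SD of change. With no such scores, the chance of a significant improvement is 2.5%.

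| Subjects analysed | Share | Shift (SD) | Chance of significant improvement |
|---|---|---|---|
| 20 | 20% | 0.10–0.20 | 6–11% |
| 20 | 40% | 0.20–0.40 | 12–31% |
| 30 | 20% | 0.10–0.20 | 7–15% |
| 30 | 40% | 0.20–0.40 | 17–47% |
| 50 | 20% | 0.10–0.20 | 9–24% |
| 50 | 40% | 0.20–0.40 | 26–72% |

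Twenty is the number of completers, so a set that includes stoppers would be larger. Fifty is a ceiling, because it also allows for screening failures.

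**6. Scale.** With 20 subjects, the change detectable with 80% power is 0.66 SD. A shift of 0.10–0.40 SD is 0.10/0.66 = 15% to 0.40/0.66 = 61% of that. In the downward case, a true change of 0.66 SD would appear as 0.66 − 0.10 = 0.56 to 0.66 − 0.40 = 0.26 SD.

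**The case against.** **A reader might infer that subjects who worsen or are hospitalised certainly stay in the CAPS data.** The documents do not support that. They are the subjects most likely to start new treatment, yet several passages in the table above say they leave the study, and section 11.B allows assessments to end. For them, collection of CAPS is unresolved. This objection stands; the point is firm only for willing subjects who stop medication.

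**The dropout sentence may already remove off-drug scores.** Someone who has stopped takes none of the doses, which is outside the 75–125% band that section 11.B applies over two consecutive visits. The sentence might therefore cover many stoppers. But it is written for non-adherence, does not say what happens to scores, and sits beside intent-to-treat and use of all available data. It leaves the gap open.

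**A reader might infer that the plan inflates riluzole's benefit.** The direction is not established. Some subjects stop because they are worse, and others may lose a real effect after stopping. Both pull the estimate down.

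**A reader might want the on-riluzole estimate to replace the planned one.** That goes too far. Post-baseline CAPS during treatment is due only at visits 6 and 12, so anyone who stops before visit 6 has no post-baseline score in that estimate. Stopping can be triggered by CGI-I or MADRS, which are not stated to be in the CAPS model, so missing at random is doubtful. The selection may favour riluzole.

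**The study is an open-label pilot, and change regardless of later treatment is a legitimate summary.** Both are true, and the second is why the planned estimate should stay. Its description as change on riluzole still does not match what it measures.

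**Conclusion.** The point holds for willing subjects who stop riluzole during the 12 weeks: their later CAPS scores can enter the single-arm estimate, and nothing planned separates them. For subjects described as leaving the study, the text conflicts.

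The bias is of unknown sign and size. Every figure for its size above rests on assumed shares and assumed effects of other treatment; the simulation covers only the upward direction and uses a simple t-test in place of the mixed model. This is a mismatch between the estimate and its description that should be corrected in the plan, not a reason to discard the data or the intent-to-treat analysis. Even after correction, a single-arm study cannot separate riluzole from natural course or regression to the mean.

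**What to change.** In the Data Analysis section:

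1. Keep the intent-to-treat mixed model as primary, and describe it, including under Aim 1, as change in CAPS after starting riluzole regardless of later treatment.
2. Prespecify one supplementary estimate from the same model that leaves out CAPS taken after the last riluzole dose plus the visit window, or after new PTSD treatment starts, whichever is earlier. State the window's length, which the Table 1 footnote does not give, and define in advance what counts as new PTSD treatment.
3. Report both estimates with the number of scores and subjects excluded. Do not let the supplementary estimate alone carry the Aim 1 claim.
4. Reconcile sections 11 (Dosing, B and C.3), Data Analysis and 12 on whether CAPS is collected after discontinuation, for each reason for stopping, and say what being a dropout in the analysis means for the scores.

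**Cost.** A few lines of text and one more model run; no change to subject care. Diary cards and pill counts help to date the last dose, and section 11, C.3 already records start and stop dates of concomitant medications. Start dates of new psychotherapy may need one added field. The supplementary estimate is less precise and is selected, for the reason given above, so it should be read only beside the primary one.
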